7.0 STATISTICAL ANALYSIS

7.1 Patient Disposition

A summary of patient disposition will display the number of patients by original NKTR-102 study entered and by dose level received in this study. The number of enrolled, discontinued from the treatment and exited the study and reasons for discontinuation will be tabulated. Disposition data will be presented in a data listing.

7.2 Protocol Deviations

Patients with important protocol deviations will be listed. Protocol deviations by severity and type will be included in the listing.

7.3 Demographics and Disease Characteristics

The following data will be summarized and listed for safety population:

Demographics (Current): age (years), sex, race, ethnicity.

Disease characteristics from Original NKTR-102: tumor type, stage, time since initial diagnosis and time since metastatic diagnosis to original NKTR-102 study will be imported from original NKTR-102 study. The values are imputed as below.

Time since initial diagnosis (years) in Original NKTR-102: $(\text{Date informed consent signed in Original NKTR -102 Study} - \text{Date of initial diagnosis}) / 365.25$, rounded to one decimal place.

Time since initial metastasis diagnosis (years) in Original NKTR-102 Study: $(\text{Date of informed consent date in Original NKTR - 102 Study} - \text{Date of diagnosis of metastatic disease}) / 365.25$, rounded to one decimal place.

7.3.1 Medical History

No medical history data was collected in current study except AE continuing from Original NKTR-102 study at study entry will be collected in AE CRF. No medical information listing will be provided.

AEs that are ongoing at the time of study entry will be summarized by SOC, preferred term and severity grade.

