#### **3.2 Secondary Objectives**

- To evaluate the safety of continued exposure to NKTR-102.
- To observe disease status and survival status in subjects receiving NKTR-102.
- To evaluate the efficacy of NKTR-102 in subjects with advanced or metastatic solid tumors.

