### 9.2 Monitoring Adverse Events

All AEs will be assessed by the Investigator and recorded in the appropriate case report form (CRF), including but not limited to, the date of onset and resolution, seriousness, severity, relationship to study drug, outcome, and action taken with study drug. Adverse events will be reported starting immediately after the subject or subject's legal representative has provided written informed consent through the End-of-Treatment visit (30 ± 7 days from the last dose of study drug in the extension study).

After providing informed consent for the extension study, if the subject is continuing in the original protocol and therefore will not have received the first dose of study drug in the extension study (Protocol 11-PIR-09), any AEs that occur will be collected under the original protocol. For subjects who have ended the original protocol and have provided informed consent for the extension study (Protocol 11-PIR-09), AEs will be collected under the extension study (Protocol 11-PIR-09).

Adverse events that were considered related to study drug in the original protocol and were ongoing when the subject ended the original protocol will be captured as a new AE in the extension study (Protocol 11-PIR-09) marked as continuing. Unrelated AEs that were ongoing at the end of the original protocol may also be captured as new AEs in the extension study (Protocol 11-PIR-09) marked as continuing.

For each AE, the following data elements will be recorded on the CRFs:

- Verbatim description of event
- NCI-CTCAE v. 4.0 grade for AE severity (refer to Section 9.3)
- Start and stop date of AE
- Relationship/causality attribution to study drug
- Whether or not the administration of study drug was reduced, interrupted, delayed, or permanently discontinued due to the AE
- Whether or not the event was considered as an SAE
- Treatment provided for the AE (pharmacologic or non-pharmacologic)
- Outcome of the AE

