### 9.3 Grading of Adverse Events

The severity of an event and the seriousness are not to be considered synonymous. The severity is grading the intensity of an event. The seriousness of event is based on the subject/event outcome or action criteria. All AEs will be assessed for severity using the NCI-CTCAE version 4.0. If a particular AE is not listed in the NCI-CTCAE, the following criteria will be used to assess severity by the Investigator:

- grade 1 = Mild (asymptomatic or mild symptoms or clinical or diagnostic observations only, intervention not indicated)

- grade 2 = Moderate (minimal, or local or non-invasive intervention indicated or limiting age-appropriate instrumental activities of daily living [ADL])
- grade 3 = Severe (medically significant but not immediately life-threatening or hospitalization or prolongation of hospitalization indicated or disabling, limiting self care ADL)
- grade 4 = Life threatening or disabling (life threatening consequences, urgent intervention indicated)
- grade 5 = Death (related to AE)

Adverse events will be reported using the maximal severity grade experienced for that continuing instance of the AE. Please refer to the CRF Completion Guidelines for detailed reporting instructions.

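### SAP 7.3.1 grades adverse events ongoing at entry by a field that holds the worst grade of the whole episode, so a carry-over event that worsens on the extension appears in the entry table at its later grade

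*SAP*

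**What the plan says.** SAP 7.3.1 explains that the extension has no medical history form. Instead, "AE continuing from Original NKTR-102 study at study entry will be collected in AE CRF", and "AEs that are ongoing at the time of study entry will be summarized by SOC, preferred term and severity grade". It does not say at what time the grade is taken.

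The record behind that table is defined in the protocol:

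- **Entry of carry-over events (Protocol 9.2).** A drug-related event still ongoing when the subject leaves the original study is "captured as a new AE in the extension study (Protocol 11-PIR-09) marked as continuing". Unrelated ongoing events may be entered in the same way.
- **Fields (Protocol 9.2).** The data elements listed for each event include one CTCAE grade, with a reference to 9.3, and one start and one stop date. A grade at entry is not among them.
- **Grade rule (Protocol 9.3).** "Adverse events will be reported using the maximal severity grade experienced for that continuing instance of the AE". The next sentence sends the reader to the CRF Completion Guidelines for details.
- **Reporting window (Protocol 9.2 and 9.5).** AE reporting runs from consent to the End-of-Treatment visit, and related events are followed longer if needed.

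SAP 6.3 defines baseline for the current study as the most recent available assessment up to and including Day 1.

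**The concern.** A table of events ongoing at entry should describe subjects as they were before the first extension dose. The grade available for it can be set at any time while the record stays open, including months into extension dosing. An on-study outcome is then read back into a baseline table.

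This matters because one stated objective is "To evaluate the safety of continued exposure to NKTR-102", and Protocol 12.2 makes safety under continued therapy the primary endpoint. Protocol 2.2 justifies the study partly by the safety data that long exposure can yield. Worsening of a toxicity the subject already had is part of that evidence. If it is presented as severity on arrival, a reader of the entry table will attribute to the original study something that happened on the extension.

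**Working it through.** The documents give no count or rate for carry-over events, so there is no plan figure to reproduce. The check follows one record through the rules and then sets out an assumed range for size.

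**Tracing one event**

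1. Fatigue, related, is Grade 1 when the subject leaves the original study. Protocol 9.2: one new extension record, flagged as continuing.
2. At Cycle 1 Day 1 it is still Grade 1. By SAP 6.3 the baseline grade is 1.
3. In Cycle 4 it reaches Grade 3 without having resolved. It is the same continuing instance, so under Protocol 9.3 the record's grade becomes 3.
4. SAP 7.3.1 selects the record because it was ongoing at entry and tabulates it by its grade: Grade 3 at entry. The grade at entry was 1.

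**Which events are affected**

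| Course of the event | Grade at Day 1 | Grade in the record | Entry table |
|---|---|---|---|
| Rises after Day 1 (e.g. 1 to 3) | 1 | 3 | too high |
| Unchanged | 1 | 1 | correct |
| Falls after Day 1 (e.g. 2 to 1) | 2 | 2 | correct |
| Peaked at 3 in the original study, 1 at Day 1, no later rise | 1 | 1 if the instance starts with the extension record; 3 if it starts in the original study | depends on the reading |

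The first row follows from the text. The last depends on what counts as the instance, which 9.3 does not define for carry-over events. The middle rows assume no higher peak in the original study, or an instance that starts with the extension record.

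**Can the worsening be recovered from the listed fields?** The record has one grade, one start date and one stop date. For a carry-over event the start date may precede the extension, and SAP 6.4 leaves a missing start day unimputed when the event is marked as continuing. The field for action taken with study drug, together with SAP 7.5, may point to a worsening that led to a dose change, but it gives neither the entry grade nor the date of the rise.

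**Illustrative size.** Let *m* be the number of carry-over records and *w* the proportion that worsen to Grade 3 or higher without resolving. Both are assumptions; the only anchor for *m* is the enrollment ceiling of 150.

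Expected wrong entries at Grade 3 or higher = *m* × *w*. Chance of at least one = 1 − (1 − *w*)^*m*, treating records as independent.

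| *m* | *w* | Expected | Chance of at least one |
|---|---|---|---|
| 30 | 1% | 30 × 0.01 = 0.3 | 1 − 0.99^30 = 0.26 |
| 60 | 5% | 60 × 0.05 = 3.0 | 1 − 0.95^60 = 0.95 |
| 90 | 10% | 90 × 0.10 = 9.0 | 1 − 0.90^90 > 0.99 |
| 90 | 15% | 90 × 0.15 = 13.5 | > 0.99 |

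For context on *w*, Protocol Table 1 gives the Grade 3 share of all reported events as 4.5/34.4 = 13.1% for fatigue, 1.9/21.6 = 8.8% for asthenia and 3.5/60.0 = 5.8% for nausea. These are shares of worst grades in another study, not rates of worsening after rollover. Diarrhea is a poor candidate, because Protocol 7.2 requires it to have been at Grade 0 for at least 7 days before dosing.

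With the grade taken at or last before Day 1, wrong entries of this kind fall to zero whatever *m* and *w* are.

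**The case against.** The strongest reply is that the governing detail may sit elsewhere. Protocol 9.3 defers to the CRF Completion Guidelines, and the SAP lists table and listing shells as an attachment. Neither is in the text available, and that text ends at SAP 7.6, before any safety section. Protocol 9.1 counts exacerbation of a pre-existing condition as an adverse event, so the guidelines could require a new record on worsening. The SAP was also written to amendment 2.0 of September 2013, whereas this protocol cites data as of May 2015, so the 9.2 and 9.3 wording should be confirmed for that version. All of this stands as a reason to check first. None of it supplies an entry grade in the documents at hand.

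Three stronger readings are tempting, and the documents do not support them:

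- *That every carry-over event whose grade changes is misgraded.* An event that only improves on the extension has its entry grade as its maximum over that period.
- *That on-study worsening is lost.* The event is entered as an extension AE at its worst grade, and Protocol 12.2 tabulates AEs by severity and maximum intensity and provides by-subject listings. What is wrong is the timing implied by the entry table, and what is missing is the date of the rise.
- *That a Grade 3 entry would show subjects enrolled against the rules.* The pre-dose condition in Protocol 6.7 and 7.2 covers only treatment-related non-hematologic toxicity and accepts a return to baseline as well as Grade 1. Screening can precede dosing by up to 28 days, and no inclusion criterion caps non-hematologic grade. The fair statement is that a reader could not tell a high grade truly present at entry from one reached later.

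**Conclusion.** The point holds as a defect in one descriptive table and in the record behind it. Read together, SAP 7.3.1 and Protocol 9.2 and 9.3 give a wrong entry grade for any carry-over event that rises after Cycle 1 Day 1 without resolving, and that conflicts with SAP 6.3. If the instance is taken to start in the original study, an earlier peak that had settled before entry is overstated as well.

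The number of records affected is unknown. The range of 0.3 to 13.5 wrong entries at Grade 3 or higher rests entirely on the assumed *m* and *w*, and its lower end is below one event. The conclusion does not depend on that range. It does depend on the unseen guidelines and shells not already capturing the entry grade or opening a new record on worsening. No hypothesis test is affected, since SAP 6.1 plans none. It should still be corrected, because safety of continued exposure is what the study is there to describe.

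**What to change.** First check the CRF Completion Guidelines and the table shells. If they already hold the grade at entry or open a new record on worsening, stating that rule in SAP 7.3.1 is enough. Otherwise:

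1. In Protocol 9.2 and the AE form, for each event marked as continuing, record the CTCAE grade at or last before Cycle 1 Day 1. Adverse events are already assessed at Screening and on Day 1, so no visit is added.
2. In SAP 7.3.1, state that the summary uses that grade, in line with the baseline definition in 6.3.
3. In Protocol 9.3 and the SAP safety analyses, record any rise above the entry grade as an on-study worsening with its own onset date and grade, and count it as treatment-emergent.

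The cost is one added CRF field, short text changes in 9.2, 9.3 and the SAP, and some extra AE records. The third step departs from the single maximal-grade record for carry-over events, so the affected safety tables need a matching rule. No dose or clinical rule changes.

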7.4 Treatments and Medications

7.4.1 Prior and Concomitant Medications

No prior and concomitant medications are collected for this study. Any use of prohibited concomitant medications will be recorded in the protocol deviation log.

7.5 Exposure

Exposure to study drug in current study will be listed and summarized in terms of exposure duration, number of cycles, cumulative dose (mg), average dose per infusion (mg/m^2), dose intensity ($\text{mg}/\text{m}^2/\text{week}$), and relative dose intensity will be calculated for treatment cycles received in this study. The number of patients with dose reduction, dose interruption, and dose delay will be tabulated along with their reason. Overall duration, cycles and cumulative dose will also be computed for all treatment received since initiation of the NKTR-102 of the Original study.

7.6 Efficacy Analysis

Tumor response will be assessed by the investigator according to the frequency that patient's standard of care allows. Baseline will be the assessment at screening visit. Data on the best response and disease progression (per physician assessment) will be collected according to RECIST criteria version 1.1 (Eisenhauser et al., 2009). Tumor assessment and responses at the baseline and subsequent visit will be presented in a listing. Best overall response (BOR) by investigator assessment will be summarized. Time to progression and survival time will be calculated from first dose of original NKTR-102 study enrollment. Time to progression is defined as time from date of first dose of original NKTR-012 study to the 1st date of progressive disease (PD) per investigator assessment in current study. Patients without PD will be censored in last visit/follow-up date. Time to death is defined as time from date of first dose of original NKTR-102 study to death date. Patients without death date will be censored in last visit/follow-up date.

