### 5.1 Inclusion Criteria

Each subject must meet the following criteria to be eligible for enrollment.

1. Subject or subject's legal representative must provide written informed consent.
2. Subject is able and willing to comply with the study visit schedule and procedures.
3. Subjects must have received prior treatment with NKTR-102 in a Nektar-sponsored study.
4. Subjects must be without signs of disease progression since receiving NKTR-102.
5. Women of childbearing potential must have a negative serum pregnancy test at screening and a negative urine pregnancy test at the predose visit of each cycle.
6. Women of childbearing potential and men who agree to use adequate contraception during study participation (at least two methods of contraception, one of which includes a barrier method [male condom] by the male partner or abstinence) or a male who has undergone a vasectomy greater than 6 months prior to Cycle 1 Day 1. Appropriate contraception must be used for at least 8 months after the last dose of the study drug on this extension study.
7. Subjects must meet requirements with respect to hematopoietic function (hemoglobin  $\geq 8.0$  g/dL or 80 g/L; absolute neutrophil count (ANC)  $\geq 1.5 \times 10^9$ /L; platelets  $\geq 75 \times 10^9$ /L).
8. Subjects must be able to receive the first dose of NKTR-102 in the extension study within 8 weeks after receiving their last dose of NKTR-102.

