6.2 Analysis Populations - Current

Enrolled Population: All patients who have provided an informed consent are included.

Safety Population: The Safety Population consists of all patients who receive at least one dose (or partial dose) of study drug (NKTR-102) under this study.

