6.3 Analytic Definitions

General:

- Age: integer of (Date informed consent signed (Current)– Date of birth) / 365.25.

- Study Day 1: Day 1 is the date of Cycle 1 Day 1 dosing date within Current study.
- Baseline (Current): Baseline will be defined as the last non-missing assessment on or before the study drug administration (Day 1).
- Study day of Current: For post-treatment events, study day is calculated as (visit/assessment date – date of current study first dose of cycle 1 study drug administration) + 1. For pre-treatment events, study day is calculated as visit date – date of Day 1. There is no study day zero.
- Study Day since First Dose of Original NKTR-102: study day is calculated as (visit/assessment date of current study – date of 1st dose of the original NKTR-102 study) + 1.
- Study Day since Last dose of Original NKTR-102: study day is calculated as (visit/assessment date of current study – date of last dose of the original NKTR-102 study) + 1.
-

Exposure

Current:

- Exposure Duration (days): Date of last dose – date of first dose (Cycle 1 Day 1) of current study + 21.
- Number of cycles: Total number of complete or partial treatment cycles the patient received.
- Cumulative dose (mg): Total actual dose (mg) the patient received across all cycles, defined as the sum of actual dose (mg) received across all cycles.
- Duration of infusion: Completion time of infusion – start time of infusion.
- Calculated cumulative dose level (mg/m^2): Cumulative dose (mg) divided by the average BSA (m^2) across all cycles.
- Dose intensity ($\text{mg}/\text{m}^2/\text{week}$): $[\text{Calculated cumulative dose level } (\text{mg}/\text{m}^2) / \text{exposure duration (days)}] \times 7$.
- Expected dose intensity ($\text{mg}/\text{m}^2/\text{week}$): initial planned dose (mg/m^2) / 3; planned dose will be 145, 120 or 95 mg/m^2 .
- Relative dose intensity (%): $\text{Dose intensity } (\text{mg}/\text{m}^2/\text{week}) / \text{Expected Dose intensity } (\text{mg}/\text{m}^2/\text{week at enrollment}) \times 100$.

Overall (Original plus Current):

The exposure duration, number of cycles, cumulative dose, calculated cumulative dose level from 1st dose exposure of the original NKTR-102 study to last exposure of current study will also be calculated.

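### SAP 7.6 starts time to progression and time to death at the original study's first dose, although only progression-free subjects could enter the extension, so any summary read as time from first dose is too long.

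*SAP*

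**What the plan says.** SAP 7.6 (Efficacy Analysis) fixes the origin for both measures: "Time to progression and survival time will be calculated from first dose of original NKTR-102 study enrollment". For survival it adds: "Time to death is defined as time from date of first dose of original NKTR-102 study to death date". The progression event that counts is the "1st date of progressive disease (PD) per investigator assessment in current study". The only incomplete-observation rule is right-censoring: "Patients without PD will be censored in last visit/follow-up date", with a matching rule for death.

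Protocol 5.1, inclusion criterion 4, sets the entry condition: "Subjects must be without signs of disease progression since receiving NKTR-102". Criterion 8 limits the gap from the last prior dose to the first extension dose to 8 weeks. Nothing limits the time since the first prior dose.

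SAP 7.6 names no population for these times. The treated population in SAP 6.2 is defined by dosing in the extension: "The Safety Population consists of all patients who receive at least one dose (or partial dose) of study drug (NKTR-102) under this study". SAP 6.3 already has an extension origin ("Day 1 is the date of Cycle 1 Day 1 dosing date within Current study") and a second clock, "Study Day since First Dose of Original NKTR-102".

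On presentation the documents leave room. SAP 7.6 says the times will be calculated and names no estimator. Protocol 12.2 sends data not otherwise mentioned to by-subject listings. SAP 6.1 says all analyses will be summarised in total and, where numbers allow, by dose level.

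**The concern.** The clock starts at a point from which subjects are not followed in this study, and being progression-free at a later point is the price of admission. The time between the two is guaranteed event-free. Right-censoring does not address this. It handles subjects whose event has not yet been seen, not those who had the event too early to be enrolled.

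Evaluating efficacy and observing survival status are secondary objectives (Protocol 3.2, SAP 3.2), and these are the only time-to-event measures in SAP 7.6. A median from original first dose would mix the wait needed to qualify for rollover with the course on the extension. It would also be easy to set beside the Phase 2 medians in Protocol 2.1.2.2, which describe unselected starters. Nothing in the summary itself would warn the reader.

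**Working it through.** There is no planned median, event count or power figure to reproduce: SAP 6.1 requires neither testing nor a specific sample size. The check has two parts.

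**Direction, from the text.** Let E be the time from original first dose to extension Cycle 1 Day 1.

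- Progression: criterion 4 rules out progression before E, and SAP 7.6 counts only progression in the extension. Every eligible dosed subject therefore has a time to progression of at least E.
- Death: every dosed subject is alive at E, so time to death is at least E.
- Subjects with an event before E are not in the data.

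A summary of these times describes T given progression-free at E, not T from first dose. It is longer whenever E exceeds zero and some starters had events before E, provided that rollover among progression-free subjects is not concentrated in those with poor prognosis.

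**Size, by illustration.** Inputs from the documents are the Phase 2 breast cancer medians in Protocol 2.1.2.2 (schedules pooled): PFS 4.7 months, used as a stand-in for time to progression, and OS 10.3 months. Assumptions are a common entry time E, a Weibull progression time with shape k, and an independent exponential post-progression time. The post-progression median is set so that OS for all starters is 10.3: 3.38, 3.83 and 4.44 months for k = 0.7, 1 and 1.5.

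- Scale: s = 4.7 / (ln 2)^(1/k), giving 7.93, 6.78 and 6.00 for k = 0.7, 1 and 1.5.
- Median time to progression from original first dose, given progression-free at E: s × [(E/s)^k + ln 2]^(1/k). For k = 1 this reduces to E + 4.7, so E = 6 gives 10.7.
- Median survival from original first dose, given progression-free at E: by numerical integration.

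| Entry E (months) | Progression, k = 0.7 / 1 / 1.5 | Survival, k = 0.7 / 1 / 1.5 |
|---|---|---|
| 1 | 7.1 / 5.7 / 5.0 | 12.7 / 11.3 / 10.6 |
| 3 | 10.3 / 7.7 / 6.2 | 15.8 / 13.3 / 11.8 |
| 6 | 14.4 / 10.7 / 8.5 | 19.9 / 16.3 / 14.1 |
| 12 | 21.8 / 16.7 / 13.9 | 27.3 / 22.3 / 19.3 |
| All starters | 4.7 | 10.3 |

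Under constant hazard the share of starters still progression-free is 2^(−E/4.7): 64%, 41% and 17% at 3, 6 and 12 months.

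**What the alternatives deliver.**

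- *From extension Cycle 1 Day 1* (subtract E from the table): for E = 3, 6, 12 the median time to progression is 4.7 throughout for k = 1; 7.3, 8.4, 9.8 for k = 0.7; and 3.2, 2.5, 1.9 for k = 1.5. Survival is 10.3 throughout; 12.8, 13.9, 15.3; and 8.8, 8.1, 7.3. This removes the guaranteed time but does not in general recover 4.7 or 10.3.
- *Delayed entry on the original clock* (subjects join the risk set at E): simulated with constant hazard, entry uniform over 0 to 12 months before selection, no censoring and 150 subjects (the Protocol 1.0 maximum). The median estimate is 4.85 months (95% range 1.65 to 6.81) against a true 4.7. Ignoring the delayed entry gives 9.62 (8.34 to 10.97). With 50 subjects the delayed-entry range is 0.27 to 8.19. If nobody enters before 3 months (uniform 3 to 12, 150 subjects) it gives 7.84 (4.92 to 9.75). The early risk sets are too small for it to be relied on.

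**The case against.** The strongest reply is that the plan never commits to a misleading summary. SAP 7.6 lists tumour assessments and summarises best response, but only calculates these two times. Protocol 12.2 points to listings, and each subject's own duration is correct. Time since first NKTR-102 exposure is a legitimate description of rollover subjects and matches the original-plus-current convention that SAP 6.1 and 6.3 use for exposure. Neither document says the result estimates the median for all starters, and the proposed origin is itself conditional on reaching the extension.

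Much of this stands. No estimator is named, neither time is a listed endpoint (Protocol 4.1.1, SAP 4.1), the study is descriptive, and the lead-in can be recovered from SAP 6.3. The supplied SAP text ends at 7.6 and the table shells (Attachment 1) are not supplied, so handling there could not be checked. The magnitudes rest on one breast cancer study and assumed entry times, while the feeder studies in Protocol 6.5 include hepatic-impairment and cardiac-function studies.

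It does not remove the problem. The rule sits under the efficacy heading with censoring rules attached, and SAP 6.1 calls for summaries, so one is to be expected. SAP 7.6 gives no delayed-entry rule, label or caveat to stop it being read as time from first dose.

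**Conclusion.** The concern holds and should be fixed. As SAP 7.6 is written, any summary of these times read as efficacy or survival from first dose is biased upward. The direction follows from the origin and the entry criterion, given a lead-in above zero, some events among starters during it, and rollover not concentrated in progression-free subjects with poor prognosis.

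The size is unknown, because the documents give no entry times. In the illustrations, entry at 3 to 12 months multiplies the median time to progression by about 1.6 to 3.6 under constant hazard (7.7/4.7 to 16.7/4.7) and median survival by about 1.3 to 2.2 (13.3/10.3 to 22.3/10.3). At 1 month the inflation is about 1 month. Other hazard shapes change the size, not the sign. No test or decision rule is touched; what is at risk is the reading of two secondary objectives.

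**What to change.** Amend SAP 7.6 as follows:

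1. Summarise time to progression and time to death from Current Study Day 1, as already defined in SAP 6.3, in the Safety Population. Describe the result as the course after extension entry, not as an estimate of the median for unselected starters.
2. If times from original first dose are also reported, label them as conditional on reaching the extension progression-free. Show the distribution of time from original first dose to Current Day 1 beside them.
3. Treat a delayed-entry analysis of time to progression as optional. If it is done, state that it assumes entry time is independent of prognosis, and show the early risk-set sizes. It does not correct survival for selection on being progression-free.

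The cost is SAP wording, a named population and one derived lead-in variable from dates the SAP already uses. No new data are needed. The summarised times will be shorter.
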